## 1.0 Objectives / Specific Aims

[figure not shown]
**Aim: Evaluate whether sonicating the Nucleus Accumbens (NAc) with transcranial focused ultrasound modifies functional connectivity between the NAc and the prefrontal cortex (PFC).**

In this single visit, open-label pilot trial, we plan to evaluate whether transcranial focused ultrasound (tFUS), delivered to the nucleus accumbens (NAc) within the magnetic resonance imaging (MRI) scanner will impact resting state functional connectivity between the NAc and functionally connected brain regions like the prefrontal cortex (PFC) and the anterior cingulate cortex (ACC) in up to 10 healthy individuals.

[figure not shown]
**HYPOTHESIS :** tFUS will reduce prefrontal cortex (PFC)-NAc functional connectivity, in healthy individuals. We will investigate this hypothesis by administering tFUS within to MRI scanner to healthy individuals and conduct resting state functional neuroimaging before- and after the tFUS stimulation.

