This open-label pilot study is investigating the basic underlying mechanism of tFUS, and evaluating whether this technology can stimulate deep brain structures associated with reward, pain, and addiction – the nucleus accumbens. We aim to use resting state neuroimaging to understand what happens to functional neural circuitry of connected brain structures to the site of stimulation.

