#### FDA Status of the BX Pulsar 1001 device.

The BX Pulsar device was initially tested at UCLA in epilepsy patients. This research required an FDA IDE, which I have attached to the IRB application. After this study was done and safety was established,

the UCLA IRB now does not require an IDE and treats this form of ultrasound just like it does regular diagnostic ultrasound, which is non-significant risk. The diagnostic ultrasound devices and this one are the same in terms of what they can produce.

Attached is the letter of approval from the UCLA for using this device in testing memory, Alzheimer's disease, coma, the amygdala and emotions, and the thalamus with healthy controls.

Additionally, the MUSC IRB1 has approved this system to investigate a new potential treatment for pain, which was shown to be safe at the proposed parameters and published recently(25). Additionally there is an ongoing trial using the same system (PI [name]) approved the IRB 1 in generalized anxiety disorder.

Importantly, this device can only deliver the power of a diagnostic ultrasound device. It is not able to deliver the power needed for High Intensity Ultrasound Ablation such as is used in neurosurgery. This would require multiple machines, precisely focused, delivering over 1000 times more energy than we are using.

In this study, up to 10 participants will receive two, 10minute sessions of either active or sham tFUS delivered to the nucleus accumbens (NAc) within the MRI environment.

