## **4.0 Study Endpoints (if applicable)**

### **Primary Outcome: Neuroimaging/Fronto-Striatal Resting State Functional Connectivity**

The main outcomes of this study are brain imaging related. Using a neuroimaging technique called resting state functional connectivity, which is a statistical dependence between time series of electro-physiological activity and (de)oxygenated blood levels in distinct regions of the brain. Functional connectivity “strength calculation” determines whether the activity between a pair of brain regions covaries or correlates over time. We will investigate the strength of the functional connectivity between the stimulation target (Nucleus Accumbens) and connected areas, including the prefrontal cortex, hippocampus, amygdala, and sensory areas of the brain at baseline, and then will determine whether tFUS increases or decreases the resting-state connectivity between these regions after the NAC has been stimulated.

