## 10.0 Study Design / Methods

- *Study Overview:* After determining eligibility and interest, written informed consent will be obtained from participants at the MUSC Center for Biomedical Imaging. Enrolled participants will be placed into the 3T MRI outfitted with a concurrent tFUS plus fMRI acquisition system (Brainsonix). First, participants will have baseline resting state functional neuroimaging conducted to quantify the functionally connected areas to the nucleus accumbens. Afterwards, while still in the MRI scanner, we will administer tFUS to the nucleus accumbens. Lastly, we conducted post-tFUS neuroimaging (same as pre-tFUS). This entire MRI procedure will take approximately 1 hour. Participants will be compensated \$100 for their time.
- *Recruitment, Screening, and Consent Procedures:* Healthy participants will be recruited from the MUSC community (students and staff) as well as general population from the greater Charleston region. We will recruit via flyers around campus, e-mail announcements and word of mouth. If interested in learning more about the study, potential subjects will be phone screened and educated regarding the study's details. If interested in participating in the study, they will be consented and enrolled into the study's protocol. We then will conduct a multi-panel urine drug screen to confirm they are not using illicit drugs and ask for their alcohol consumption (>3 drinks per day is exclusionary).
- *Pregnancy Test Procedures:* If participants are individuals biologically capable of becoming pregnant, they will be provided with a pregnancy test strip. After completing the pregnancy test, participants with negative results will be asked to continue to the remaining study procedures, whereas those with a positive result will be debriefed and released.
- *tFUS Procedures:* All tFUS will be administered in similar mythology to that in our prior published work (25). Within the MRI scanner, participants receive two, 10-min sessions of either active or sham tFUS spread 10 min apart targeting the nucleus accumbens [fundamental frequency: 650 kHz, Pulse repetition frequency: 10 Hz, Pulse Width: 5 ms, Duty Cycle: 5%, Sonication Duration: 30s, Inter-Sonation Interval: 30 s, Number of Sonifications: 10, ISPTA.0 995 mW/cm^2, ISPTA.3 719 mW/cm^2, Peak rarefactional pressure 0.72 MPa].

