- *Sham tFUS Procedures:* Participants will be randomized to receive either two, 10 minute active tFUS sessions, or two 10 minute sham tFUS sessions within the scanner. The sham sessions will include a transducer that is connected in a similar fashion to that of active tFUS, however the cable will not be plugged into the system, thus no ultrasound will be delivered to the participant. Participants will not know or be told whether they are receiving active- or sham- tFUS.
- *Neuroimaging Procedures:* All MRI imaging will be performed using a Siemens 3.0 T Prisma scanner equipped with a 32-channel head coil. MRI data will be acquired from all participants before and after tFUS administration. All MRI scan visits will be held at the MUSC Center for Biomedical Imaging (CBI; see the Facilities and Resources section). Each MRI scan session will include a high-resolution T1-weighted structural scan (whole brain sagittal acquisition, 224 slices, TR=2530ms,

TE=3.65ms, TI=1100ms, 1mm thick slices, FOV=256, 256x176, flip angle = 7 degrees.), followed by 24 minutes of resting-state scanning, then a concurrent tFUS/fMRI paradigm, and lastly, 24 more minutes of post-tFUS resting-state scanning. All functional scans will use the high-resolution fMRI protocol described in the Preliminary Study: whole brain acquisition, 136 axial slices, 1.5x1.5x1.5mm voxel size, TR=2000ms, TE=30ms, FOV=204mm, multi-band factor=3.

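### The protocol calls itself open-label and frames its hypothesis as before versus after tFUS, yet it randomises participants to active or sham and conceals the allocation from them

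*Protocol*

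**What the plan says.** The protocol contains two descriptions of the design.

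**An open-label before/after study**
- Section 1.0 opens the aim with "In this single visit, open-label pilot trial". Section 2.0 repeats the label: "This open-label pilot study is investigating the basic underlying mechanism of tFUS".
- Section 1.0 says the hypothesis will be investigated by "administering tFUS within to MRI scanner to healthy individuals and conduct resting state functional neuroimaging before- and after the tFUS stimulation". No control condition is named.
- Section 4.0 says that, after a baseline measurement, the investigators "will determine whether tFUS increases or decreases the resting-state connectivity between these regions after the NAC has been stimulated".
- The Study Overview in section 10.0 gives the sequence as baseline scan, tFUS to the nucleus accumbens (NAc), post-tFUS scan. It mentions neither sham nor randomisation.

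**A randomised, participant-blinded, sham-controlled study**
- Section 3.0, under the FDA status of the device: "up to 10 participants will receive two, 10minute sessions of either active or sham tFUS".
- Section 10.0, tFUS Procedures: "participants receive two, 10-min sessions of either active or sham tFUS".
- Section 10.0, in its paragraph on the sham, states: "Participants will be randomized to receive either two, 10 minute active tFUS sessions, or two 10 minute sham tFUS sessions within the scanner". For the sham, "the cable will not be plugged into the system, thus no ultrasound will be delivered to the participant". The same paragraph says participants will be unaware of their allocation.

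Section 6.0 sets enrolment at up to 10 in total. It gives no split by arm.

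**The concern.** A trial that randomises participants and hides the allocation from them is not open-label. The conflict goes beyond the label. Sham participants receive no ultrasound, so their NAc is never stimulated, and the hypothesis and primary outcome as worded describe the active arm only.

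The meaning of the primary result is at stake. A before/after change in stimulated participants mixes any effect of tFUS with whatever else changes over a long scanning session. Section 10.0 puts 24 minutes of resting-state scanning before the tFUS block and 24 minutes after it. A sham arm would separate the two, but the aim, hypothesis and primary outcome never name the active-versus-sham comparison. The choice among an active-only change, a pooled change and a between-arm difference is therefore left open, and could be made after the data are seen. Nor can a reader tell whether all participants or only some receive ultrasound.

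**Working it through.** The protocol gives no alpha, power, effect size, SD or allocation ratio, so there is no stated figure to reproduce. The finding rests on comparing the text; the arithmetic only shows the consequence.

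**Side by side**

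| Feature | Sections 1.0, 2.0, 4.0 | Section 10.0 (tFUS and Sham Procedures), section 3.0 |
|---|---|---|
| Label | Open-label | Participants unaware of allocation |
| Allocation | None mentioned | Randomised, active or sham |
| Who is stimulated | Everyone, as worded | Active arm only |
| Contrast named | Before versus after | None |

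Blinding is described for participants only, so the right-hand column is at least single-blind. That is already incompatible with the label on the left.

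**What each before/after contrast estimates.** Let c be the change that would occur without ultrasound and δ the added effect of tFUS.
- Active arm only: c + δ.
- All participants pooled, assuming 5 active and 5 sham: [5(c + δ) + 5c] / 10 = c + δ/2.
- Active minus sham: (c + δ) − c = δ.

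Only the last isolates the tFUS effect, and it is the one the protocol does not name.

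**Precision under each reading.** Assumptions not in the protocol: all 10 places filled, the splits shown, and equal SD of the change score in both arms. Half-widths of the 95% confidence interval are in units of that SD.

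Before/after, formula t(0.975, n−1)/√n:
- n = 10: 2.262/√10 = 0.715
- n = 5 (active arm alone): 2.776/√5 = 1.242

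Active versus sham, formula t(0.975, 8) × √(1/a + 1/b), with t = 2.306:
- 5 versus 5: 2.306 × √0.400 = 1.458
- 6 versus 4: 2.306 × √0.417 = 1.489
- 7 versus 3: 2.306 × √0.476 = 1.591
- 8 versus 2: 2.306 × √0.625 = 1.823

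At 5 versus 5 the between-arm interval is about twice as wide as the before/after interval in 10 (1.458/0.715 = 2.04). The two answer different questions, so the narrower interval is no argument for the before/after design. Enrolment below 10 would widen all of them.

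**The case against.** The strongest reply is that section 1.0 states no statistical test. It says how data will be obtained, and scanning before and after is exactly what a between-arm comparison of change would need. On this view tFUS is shorthand for either condition. The Neuroimaging Procedures do use it that way, since all participants are scanned before and after it. The between-arm contrast might also stand in a statistical analysis plan that was not available for this review.

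Part of this stands. The shorthand reading is plausible for the Study Overview, and the absence of analysis detail is not the complaint. But shorthand cannot cover a hypothesis that tFUS reduces connectivity, or an outcome defined after the NAc has been stimulated, because an unplugged transducer stimulates nothing. An analysis plan could add a contrast, but it would not remove the protocol's own conflict over label, randomisation and blinding.

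A second reply is that the sham text may have been carried over. Section 10.0 says the procedures follow the group's earlier published work, and the reference list shows that work as a double-blind, sham-controlled study. This is possible, and it is why the sponsor must say which design is meant. It does not make the current text consistent.

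Third, the precision figures rest on an assumed sample size and split. That is correct, and they are offered only as illustration.

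**Conclusion.** The concern holds, and it must be fixed before the results can be interpreted. The protocol describes two incompatible designs, and its aim, hypothesis and primary outcome belong to the one without a control. The detailed procedures lean towards a randomised sham-controlled trial that is wrongly labelled and framed, but the document alone cannot settle this.

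One consequence follows from the text without further assumption: if the randomisation stands, not all of those enrolled receive ultrasound. The roughly twofold difference in interval width depends on 10 participants, a 5/5 split and equal SDs. For a pilot of this size, low precision is not a separate criticism.

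**What to change.** The sponsor should confirm the intended design and align sections 1.0, 2.0, 3.0, 4.0 and 10.0 with it. Section 12.0 also needs checking, because it says those taking part will be receiving tFUS and will know this before they agree to participate.

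**If the trial is randomised:**
- Replace the open-label description in sections 1.0 and 2.0 with: randomised, participant-blinded, sham-controlled.
- Say active or sham tFUS in the Study Overview.
- State the primary contrast in sections 1.0 and 4.0 as the active-versus-sham difference in pre-to-post change in NAc–PFC connectivity. This is the pair already named in the hypothesis. How the other regions listed in section 4.0 are handled is a separate matter.

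**If the trial is single-arm:**
- Remove the randomisation, sham and blinding text from sections 3.0 and 10.0.
- State in sections 1.0 and 4.0 that the before/after change is uncontrolled and cannot by itself be attributed to tFUS.

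The edits are to wording only. No participants or scans are added, since section 10.0 already images everyone before and after. The design choice does have a price. The randomised version means fewer participants receive active tFUS and the between-arm estimate is imprecise. The single-arm version gives up attribution of the change to tFUS.

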## 2.0 Background

Currently, several brain stimulation approaches have attempted to modulate pain, mood, and behavior with limited success. The two most studied approaches are transcranial magnetic stimulation (TMS) and transcranial direct current stimulation (tDCS). TMS, which is FDA approved for treating depression and OCD, can only stimulate the surface of the brain and can only stimulate deeper by increasing the intensity, and spreading the field. It is thus not deep and focal but deep and broad. Unlike TMS, which is a cortical stimulation approach, deep brain stimulation (DBS), which is FDA approved for treating Parkinson's Disease (PD), can stimulate deep in the brain with high spatial specificity. DBS has been also investigated experimentally to manage neuropathic pain; however, the surgical risk and implantation of the electrodes are semi-permanent and arguably not worth the benefit. Lastly there is tDCS, a low cost, low-amplitude electric current delivered to the scalp and ultimately through brain. tDCS is not powerful enough to depolarize neurons, although it has been demonstrated to influence the level of excitability and modulate the firing rate of individual neurons. Of all brain stimulation approaches, there is a need for a safe, noninvasive, focal, and effective approach that can reliably modulate neural tissue. This proposal addresses this gap, by advancing transcranial focused ultrasound (tFUS), a technological advancement on the forefront of neuroscience and neuromodulation (Figure 2).

**Functionally connected areas of the Nucleus Accumbens (NAc).** Key emotional, pain, and reward systems are connected through the NAc, including the insula, dorsal anterior cingulate cortex (dACC), prefrontal cortex (PFC), thalamus (Tha), amygdala (Amy), and periaqueductal gray (PAG). Additionally, the NAc receives excitatory inputs from the ventromedial PFC, dACC, amygdala, and hippocampal formation (not shown) and dopaminergic inputs from the ventral tegmental area (VTA) of the midbrain.

[figure not shown]
**Figure 2.** On the right, the electric fields produced by tDCS and TMS are presented. These two commonly utilized forms of brain induce biologically active electrical fields in broad (>4cm) cortical targets. Alternatively, tFUS (right) has the capability to focally deliver energy to cortical and subcortical tissue with <1cm resolution.(33)

This open-label pilot study is investigating the basic underlying mechanism of tFUS, and evaluating whether this technology can stimulate deep brain structures associated with reward, pain, and addiction – the nucleus accumbens. We aim to use resting state neuroimaging to understand what happens to functional neural circuitry of connected brain structures to the site of stimulation.

### 3.0 Intervention to be studied (if applicable)

#### Transcranial Focused Ultrasound (tFUS)

Transcranial focused ultrasound (tFUS) is a promising new technology that is both noninvasive and may be focally applied to deep brain targets(1-4) (**Figure 3**). tFUS utilizes transducers which contain piezoelectric elements to produce pulses of ultrasonic waves that summate deep in the brain(5-7). tFUS noninvasively stimulates deep brain targets with a high level of spatial resolution. No other current technologies exist for noninvasive deep brain stimulation which makes tFUS a highly promising technology that may have substantial research and clinical potential(1, 4, 8-12). Transcranial focused ultrasound (tFUS) uses a single large concave transducer fixed in a head-worn apparatus on the scalp to produce ultrasonic waves (650kHz) pulsed in 30 second intervals. Unlike traditional diagnostic ultrasound, which constantly transmits ultrasound and ‘listens’ to the echo to form an image, tFUS delivers the ultrasound in trains or short bursts of pulses. It is still unclear whether tFUS, at the FDA-prescribed power limits, depolarizes neurons, however it is hypothesized that tFUS acts on neurons via a mechanical force mechanism of action, leading to increased conductance of neurons and opening of ion channels(13).

**Figure 3.** Screenshots from our custom-made software (47) used to show the tFUS transducer (left) placed on the scalp, and (right) the theoretical peak sonication area deep within the brain based on the fixed focal length of the specific transducer used.

**Figure 4.** transcranial focused ultrasound (tFUS) holder system containing the tFUS transducer.

Due to the inherent fundamentals of the waveform of ultrasonic forces, tFUS maximal energy can be focused both deep in the brain (2-12cm under the cap; for comparison, traditional TMS can stimulate 1-3.4cm^2 deep(14, 15)) and focally (as small as 0.5mm in diameter, and up to 1000mm; the facility of a standard, commercially-available 70mm figure-of-8 TMS coil is roughly 50mm^2 (14, 15)). Furthermore, tFUS has been demonstrated to safely stimulate neural tissue(12, 16-18), proposing cellular mechanisms for its efficacy(12, 18-23), and now is being used in human patients(24). Recently, tFUS administered to the thalamus of coma patients was demonstrated to assist in recovery of consciousness(24). Thus, tFUS is an extremely promising, new form of noninvasive deep brain stimulation that can be focused on deep brain structures to elicit meaningful behavioral responses. This proposal plans to use tFUS, administered to deep brain structures involved in reward and pain, to produce changes in brain functional connectivity.

We will be using the Brainsonix Low intensity focused ultrasound pulsation device. (BX Pulsar 1001). Please see the manufacturers description (Technical Summary) along with appendixes about the actual safety of the device itself.

#### FDA Status of the BX Pulsar 1001 device.

The BX Pulsar device was initially tested at UCLA in epilepsy patients. This research required an FDA IDE, which I have attached to the IRB application. After this study was done and safety was established,

the UCLA IRB now does not require an IDE and treats this form of ultrasound just like it does regular diagnostic ultrasound, which is non-significant risk. The diagnostic ultrasound devices and this one are the same in terms of what they can produce.

Attached is the letter of approval from the UCLA for using this device in testing memory, Alzheimer's disease, coma, the amygdala and emotions, and the thalamus with healthy controls.

Additionally, the MUSC IRB1 has approved this system to investigate a new potential treatment for pain, which was shown to be safe at the proposed parameters and published recently(25). Additionally there is an ongoing trial using the same system (PI [name]) approved the IRB 1 in generalized anxiety disorder.

Importantly, this device can only deliver the power of a diagnostic ultrasound device. It is not able to deliver the power needed for High Intensity Ultrasound Ablation such as is used in neurosurgery. This would require multiple machines, precisely focused, delivering over 1000 times more energy than we are using.

In this study, up to 10 participants will receive two, 10minute sessions of either active or sham tFUS delivered to the nucleus accumbens (NAc) within the MRI environment.

## **4.0 Study Endpoints (if applicable)**

### **Primary Outcome: Neuroimaging/Fronto-Striatal Resting State Functional Connectivity**

The main outcomes of this study are brain imaging related. Using a neuroimaging technique called resting state functional connectivity, which is a statistical dependence between time series of electro-physiological activity and (de)oxygenated blood levels in distinct regions of the brain. Functional connectivity “strength calculation” determines whether the activity between a pair of brain regions covaries or correlates over time. We will investigate the strength of the functional connectivity between the stimulation target (Nucleus Accumbens) and connected areas, including the prefrontal cortex, hippocampus, amygdala, and sensory areas of the brain at baseline, and then will determine whether tFUS increases or decreases the resting-state connectivity between these regions after the NAC has been stimulated.

